#### **7.3.5.2. Non-Gilead Concomitant Therapy Report**

Special situations involving non-Gilead concomitant medications does not need to be reported on the SSR form; however, for special situations that result in AEs due to a non-Gilead concomitant medication, the AE should be reported on the AE form.

Any inappropriate use of concomitant medications prohibited by this protocol should not be reported as “misuse,” but may be more appropriately documented as a protocol deviation.

All clinical sequelae in relation to these SSRs will be reported as AEs or SAEs at the same time using the AE eCRF and/or the SAE report form. Details of the symptoms and signs, clinical management, and outcome will be reported, when available.

## 7.4. Reporting Process for Serious Adverse Events and Special Situation Reports

### 7.4.1. Serious Adverse Event Reporting Process

For fatal or life-threatening events, copies of hospital case reports, autopsy reports, and other documents are also to be transmitted by email or fax when requested and applicable. Transmission of such documents should occur without personal subject identification, maintaining the traceability of a document to the subject identifiers.

Additional information may be requested to ensure the timely completion of accurate safety reports.

Any medications necessary for treatment of the SAE must be recorded onto the concomitant medication section of the subject's eCRF and the SAE narrative section of the Safety Report Form eCRF.

#### 7.4.1.1. Electronic Serious Adverse Event Reporting Process

- Site personnel will record all SAE data on the applicable eCRFs and from there transmit the SAE information to Gilead GLPS within 24 hours of the investigator's knowledge of the event from ICF signature throughout the duration of the study, including the protocol-required posttreatment follow-up period.

If it is not possible to record and transmit the SAE information electronically, record the SAE on the paper SAE reporting form and transmit within 24 hours:

Gilead GLPS

Email: PPD [REDACTED]

or

Fax: PPD [REDACTED]

If an SAE has been reported via a paper form because the eCRF database has been locked, no further action is necessary. If the database is not locked, any SAE reported via paper must be transcribed as soon as possible on the applicable eCRFs and transmitted to GLPS.

## 7.4.2. Special Situations Reporting Process

### 7.4.2.1. Paper Special Situations Reporting Process for Study Drug

- All SSRs will be recorded on the special situations report form and transmitted by emailing or faxing the report form within 24 hours of the investigator's knowledge of the event to the attention of Gilead GLPS from study drug initiation throughout the duration of the study, including the protocol-required posttreatment follow-up period.

Gilead GLPS

Email: PPD

or

Fax: PPD

### 7.4.2.2. Reporting Process for Gilead Concomitant Medications

Special situations that involve Gilead concomitant medications that are not considered study drug must be reported within 24 hours of the investigator's knowledge of the event to Gilead GLPS utilizing the paper special situations report form to:

Gilead GLPS

Email: PPD

or

Fax: PPD

Any inappropriate use of concomitant medications prohibited by this protocol should not be reported as "misuse," but may be more appropriately documented as a protocol deviation.

Special situations involving non-Gilead concomitant medications do not need to be reported on the SSR form; however, special situations that result in AEs due to a non-Gilead concomitant medication, must be reported as an AE.

### 7.4.2.3. Pregnancy Reporting Process

The investigator should report pregnancies in female study subjects and/or female partners of male subjects that are identified after initiation of study drug and throughout the study, including the after study drug follow-up period, to Gilead GLPS using the pregnancy report form within 24 hours of becoming aware of the pregnancy. Contact details for transmitting the pregnancy report form are as follows:

Gilead GLPS

Email: PPD

or

Fax: PPD

The pregnancy itself is not considered an AE, nor is an induced elective abortion to terminate a pregnancy without medical reasons.

All other premature terminations of pregnancy (eg, a spontaneous abortion, an induced therapeutic abortion due to complications or other medical reasons) must be reported within 24 hours as an SAE, as described in Section 7.4.1. The underlying medical reason for this procedure should be recorded as the AE term.

A spontaneous abortion is always considered to be an SAE and will be reported as described in Section 7.4.1. Furthermore, any SAE occurring as an adverse pregnancy outcome after study must be reported to the Gilead GLPS.

The subject should receive appropriate monitoring and care until the conclusion of the pregnancy. The outcome of the pregnancy/partner pregnancy should be reported to Gilead GLPS using the pregnancy outcome report form. If the end of the pregnancy/partner pregnancy occurs after the study has been completed, the outcome should be reported directly to Gilead GLPS. Gilead GLPS contact information is as follows: email: PPD and fax: PPD .

Refer to [Appendix 5](#) for Pregnancy Precautions, Definition for Female of Childbearing Potential, and Contraceptive Requirements.

## 7.5. Gilead Reporting Requirements

Depending on relevant local legislation or regulations, including the applicable US FDA Code of Federal Regulations, the EU Clinical Trials Directive (2001/20/EC) and relevant updates, and other country-specific legislation or regulations, Gilead may be required to expedite to worldwide regulatory agencies reports of SAEs which may be in the form of line-listings, serious adverse drug reactions (SADRs), or suspected unexpected serious adverse reactions (SUSARs). In accordance with the EU Clinical Trials Directive (2001/20/EC), Gilead or a specified designee will notify worldwide regulatory agencies and the relevant IEC in concerned Member States of applicable SUSARs as outlined in current regulations.

Assessment of expectedness for SAEs will be determined by Gilead using reference safety information specified in the IB or relevant local label as applicable.

All investigators will receive a safety letter notifying them of relevant SUSAR reports associated with any study drug. The investigator should notify the IRB or IEC of SUSAR reports as soon as is practical, where this is required by local regulatory agencies, and in accordance with the local institutional policy.

### **7.5.1. Clinical Laboratory Abnormalities and Other Abnormal Assessments as Adverse Events or Serious Adverse Events**

Laboratory abnormalities without clinical significance are not recorded as AEs or SAEs. However, laboratory abnormalities (eg, clinical chemistry, hematology, and urinalysis) that require medical or surgical intervention or lead to study drug interruption, modification, or discontinuation must be recorded as an AE, as well as an SAE, if applicable. In addition, laboratory or other abnormal assessments (eg, ECG, X-rays, vital signs) that are associated with signs and/or symptoms must be recorded as an AE or SAE if they meet the definition of an AE or SAE as described in Sections 7.1.1 and 7.1.2. If the laboratory abnormality is part of a syndrome, record the syndrome or diagnosis (eg, anemia), not the laboratory result (ie, decreased hemoglobin).

For specific information on handling of clinical laboratory abnormalities in this study, please refer to Section 7.6.

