#### 3.2.1.1. DLT Definition

A DLT is any toxicity defined below excluding toxicities clearly related to disease progression or disease-related processes occurring during the DLT assessment window (Day 1 through Day 21):

- Grade  $\geq$  4 neutropenia (absolute neutrophil count [ANC]  $<$  500/mm^3)
- Grade  $\geq$  3 neutropenia (ANC  $<$  1000/mm^3) with fever (a single temperature of  $>$  38.3°C or a sustained temperature of  $\geq$  38°C for more than 1 hour)
- Grade  $\geq$  3 thrombocytopenia
- Grade  $\geq$  2 bleeding (eg, GI, respiratory, epistaxis, or purpura)
- Grade  $\geq$  3 anemia
- Grade  $\geq$  3 or higher non-hematologic toxicity, except:
  - Grade 3 nausea or emesis with maximum duration of 48 hours on adequate medical therapy
  - Grade 3 diarrhea which persists for  $<$  72 hours in the absence of maximal medical therapy.
- Grade  $\geq$  2 non-hematologic TEAE that in the opinion of the investigator is of potential clinical significance such that further dose escalation would expose subjects to unacceptable risk
- Continuous treatment interruption of  $\geq$  7 days due to unresolved toxicity
- Any toxicity event that precludes further administration of GS-4224

- Any Grade 3 or Grade 4 elevation in aspartate aminotransferase (AST) or alanine aminotransferase (ALT) associated with a Grade 2 elevation in bilirubin lasting  $\geq 7$  days
- An irAE for which immunotherapy should be permanently discontinued (eg, any grade encephalitis, Grade 3 myocarditis, reoccurrence of the same Grade 3 adverse reaction).

For certain toxicities, such as laboratory assessments without a clear clinical correlate, a discussion between the investigator and medical monitor may take place to determine if this AE should be assessed as a DLT.

Excluded from this definition:

- Grade 3 AEs of tumor flare (defined as local pain, irritation, or rash localized at sites of known or suspected tumor)
- Grade 3 rash without systemic signs or symptoms
- Grade 3 irAE that resolves to a Grade 1 or less within 21 days, except as described above.

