#### 5.4.2. Treatment Interruption for GS-4224

The following qualifying AEs must lead to interruption of GS-4224 administration, unless there is another obvious attribution (eg, trauma, PD):

- Dose interruption should occur for Grade  $\geq 3$  serum creatinine (more than  $3\times$  baseline) toxicity;
- Dose interruption should occur in subjects with any Grade 3 or Grade 4 elevation in AST or ALT associated with a Grade 2 elevation in bilirubin;
- Any Grade  $\geq 3$  non-skin, drug-related AE with the following exceptions:

Do not interrupt treatment for Grade  $\geq 3$  fatigue

- Any Grade  $\geq 3$  drug-related laboratory abnormality with the following exceptions for lymphopenia:

Grade 3 lymphopenia does not require a dose interruption

- Any AE, laboratory abnormality, or intercurrent illness which, in the judgment of the investigator, warrants interrupting the dose of study drug

Subjects receiving GS-4224 who have drug-related toxicities that meet the criteria for dose interruption should have GS-4224 interrupted until criteria to resume treatment are met.

**Note:** GS-4224 should be discontinued in subjects who experience any Grade  $\geq 3$  skin drug-related AE with systemic signs or symptoms or suspected Stevens-Johnson syndrome (SJS) or toxic epidermal necrolysis (TEN).

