2. PLANNED ANALYSIS

2.1. Interim Analysis

2.1.1. Analyses for Dose Escalation Decisions

To support dose escalation decision, safety data, including DLTs and other AEs will be listed and summarized, if appropriate. Supportive data including demographic, disease history, concomitant medication, and drug administration will be listed. The analysis will occur when all subjects enrolled in a dose level have been followed for at least 21 days after the first dose of GS-4224 or two DLTs have been observed, whichever is earlier.

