7.1.7. Definition and Analysis of Dose Limiting Toxicity

Toxicity will be graded according CTCAE Version 5.0. A DLT is any toxicity specified in the study protocol occurring during the DLT assessment window (Day 1 through Day 21).

DLTs occurred within the 21-Day DLT observation period will be summarized by PT in descending order of total frequency for the DLT-Evaluable Analysis Set. Toxicities that meet the criteria of DLTs and occur beyond the first 21 days observation period (ie. DLT-type AEs) will also be summarized for the Safety Analysis Set by PT only in descending order of total frequency.

In addition, by-subject data listings will be provided by cohort and subject ID number in ascending order for the following:

- Dose Limiting Toxicities
- DLT-type AEs: toxicities that met the criteria of DLTs and occurred beyond the first 21 days observation period during study

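### A DLT-grade laboratory value judged clinically insignificant and attributed to neither drug nor disease can miss the AE record, and so the DLT count

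*Protocol*

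**What the plan says.** - **DLT definition (Protocol 3.2.1.1).** Several criteria are laboratory grades: neutropenia at Grade 4 or higher, thrombocytopenia and anemia at Grade 3 or higher, and a combined transaminase and bilirubin criterion. Only toxicity clearly due to the disease is excluded. For some toxicities, "such as laboratory assessments without a clear clinical correlate, a discussion between the investigator and medical monitor may take place" to settle whether the AE counts as a DLT.
- **AE recording (Protocol 7.5.1).** "Laboratory abnormalities without clinical significance are not recorded as AEs or SAEs". The next sentence requires an AE for abnormalities that need medical or surgical intervention, or that "lead to study drug interruption, modification, or discontinuation must be recorded as an AE". The section then refers to 7.6 for specifics; 7.6 only names the grading scale.
- **Interruption (Protocol 5.4.2).** "The following qualifying AEs must lead to interruption of GS-4224 administration", unless another cause is obvious. The list includes any Grade 3 or higher "drug-related laboratory abnormality with the following exceptions for lymphopenia", and Grade 3 or 4 "elevation in AST or ALT associated with a Grade 2 elevation in bilirubin".
- **DLT analysis (SAP 7.1.7).** "DLTs occurred within the 21-Day DLT observation period will be summarized by PT in descending order of total frequency", in the DLT-Evaluable Analysis Set. Under SAP 7.1.1, preferred terms come from coding AEs.
- **Escalation package (SAP 2.1.1).** DLTs and other AEs are given as examples of the safety data. "Supportive data including demographic, disease history, concomitant medication, and drug administration will be listed".

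**The concern.** DLT incidence is the primary endpoint, and it drives both escalation and the MTD. Some DLT criteria are met by a laboratory grade alone. The rule that decides whether a laboratory result becomes an AE uses a different test, clinical significance, which the protocol does not define and the investigator applies in an open-label trial. The DLT table is built on AE terms. Where the two tests disagree, a result can satisfy the DLT definition and still leave no record from which it would be tabulated.

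The optional discussion in Protocol 3.2.1.1 does not close this, because it takes for granted that the finding is already an AE. Neither the protocol nor the SAP checks graded laboratory data against the recorded DLTs.

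**Working it through.** No figure in the plan is at issue, so the check follows a Days 1 to 21 laboratory value through the rules.

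**Step 1. Which laboratory values are DLTs on grade?** Chiefly the hematologic ones. The general non-hematologic criterion speaks of toxicity, and an asymptomatic chemistry value is a natural candidate for the discussion with the medical monitor.

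**Step 2. Which of these must become AEs?**

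| Situation | Route to an AE record |
|---|---|
| Grade 3 or higher, judged drug-related | 5.4.2 requires interruption, so 7.5.1 requires an AE |
| Grade 3 or higher creatinine, or Grade 3 or 4 AST/ALT with Grade 2 bilirubin | Same route; these 5.4.2 items carry no drug-related qualifier and yield only to another obvious cause |
| Needs intervention, such as transfusion | 7.5.1, intervention limb |
| Has signs or symptoms and meets the AE definition | 7.5.1, symptom limb |
| Investigator interrupts on judgment | 5.4.2 last item, then 7.5.1 |
| Hematologic DLT grade, not drug-related, not clearly disease, untreated, no symptoms, no interruption, judged insignificant | None stated |

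The only laboratory exemption from interruption is Grade 3 lymphopenia, which is not among the named hematologic DLT criteria. The first route assumes the interruption takes place. The 5.4.2 list is also headed as a list of AEs, which is slightly circular for a laboratory value not yet recorded as one.

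**Step 3. How can the last row arise?** The DLT definition does not ask for drug-relatedness; the general laboratory item in 5.4.2 does. Protocol 7.2.1 gives concomitant medication, intercurrent illness and preexisting conditions as examples of alternative causes. A Grade 3 platelet count put down to a concomitant medication is neither drug-related nor disease-related, yet it meets 3.2.1.1.

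**Step 4. How is that subject analyzed?** SAP 3.1.4 admits a subject who took at least 16 of 21 doses and had safety assessments, including chemistry and hematology, through the window. A subject in the last row who meets this enters the denominator with no DLT. Non-recording cannot add a DLT, so the error runs one way.

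**Step 5. What does one lost event change?** Under Protocol 3.2.1:
- 1 of 3 becomes 1 − 1 = 0 of 3: escalation may proceed without the 3 further subjects.
- 2 of 6 becomes 2 − 1 = 1 of 6: the dose meets the MTD limit instead of triggering de-escalation.
- At 1000 mg BID, 2 of 6 becoming 1 of 6 also removes the bar on enrolling the additional 14 subjects.

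**The case against.** The strongest reply is that the protocol already captures nearly all of these events. The sentence after the one quoted from 7.5.1, read with 5.4.2, covers every drug-related Grade 3 or higher value. Protocol 7.2.1 allows a judgment of unrelated only where there is evidence of another cause. The endpoint is defined by Section 3.2, not by the AE form. Laboratory results also stay in the data: SAP 7.2 lists them with grade flags, and SAP 7.2.1 grades central and local values. Most of this stands, and it rules out several stronger readings.

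- A reader might infer that laboratory-defined DLTs in general drop out of the primary endpoint. The capture rules above show they do not.
- A reader might infer that 5.4.2 helps only with values called drug-related. The creatinine and the transaminase-with-bilirubin items say otherwise.
- A reader might infer from SAP 2.1.1 that the safety review team would not see laboratory data. The wording there is not exhaustive, Protocol 3.2.3 leaves the required data to the SRT Charter, and the charter is not among the documents.
- A reader might want to attach a percentage to the problem. Any per-subject rate would be an assumption with no support in the documents.

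The visibility argument stands only in part. The summary in SAP 7.2.1.2 takes the worst grade up to 30 days after the last dose; it is neither confined to Days 1 to 21 nor linked to DLT status. Protocol 8.7.3 promises separate listings and summaries of Grade 3 or higher laboratory abnormalities. The SAP does not specify them, although SAP 7.7 declares no deviation. Protocol 6.2.9 requires a local result unsupported by the central laboratory to be reported on the eCRF when it causes a dose change or forms part of an AE assessment. It states no such route for a local-only value that does neither.

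**Conclusion.** The point holds for a narrow subset: DLT-grade values, chiefly hematologic, that are attributed to neither study drug nor clearly disease, are untreated, and are judged not clinically significant. For these, Protocol 3.2.1.1 and 7.5.1 conflict, and the SAP has no step that would reveal it.

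The direction is certain, since DLTs can only be under-counted. The frequency is unknown and may be small. The case for acting rests on the weight of a single event in blocks of 3 and 6, not on an expected number of events. Some of these values might properly be ruled not to be DLTs after discussion; the defect is that neither the decision nor its reason need be on record.

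This assumes that DLTs reach the table through coded AE records, as SAP 7.1.1 and 7.1.7 imply. The documents do not say whether the eCRF captures DLTs on a separate form. If it does, and that form is completed independently of the AE form, the gap is smaller.

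**What to change.** 1. **Protocol 7.5.1.** Reconcile it with 3.2.1.1 by stating that any laboratory value on Days 1 to 21 that meets a 3.2.1.1 criterion is recorded as an AE, with its DLT decision and the reason, whatever its judged significance or relatedness. This is a recording rule and leaves the DLT criteria and treatment rules as they are.
2. **SAP 7.1.7.** Add a programmed listing of all DLT-grade laboratory values on Days 1 to 21, central and local, for subjects in the escalation cohorts. Reconcile each with the recorded DLTs: counted, or not counted and why.

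SAP Section 1 reports that the study was terminated early during Phase 1b, so escalation has ended and the listing is the main remaining action. If the SAP is already final, the same section provides for documenting the change in the CSR.

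The cost is one protocol sentence, one listing, and a few more AE entries in Cycle 1.

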### **7.6. Toxicity Management**

Severity should be recorded and graded according to NCI-CTCAE version 5.0 ([Appendix 4](#)).

## 8. STATISTICAL CONSIDERATIONS

### 8.1. Analysis Objectives and Endpoints

#### 8.1.1. Analysis Objectives

The primary objectives of this study are as follows:

##### Phase 1b Dose Escalation

- Characterize the safety and tolerability of GS-4224 in subjects with advanced solid tumors
- Determine the MTD and RP2D of GS-4224 in subjects with advanced solid tumors

The secondary objectives of this study are as follows:

##### Phase 1b Dose Escalation

- Evaluate the PK of GS-4224 in subjects with advanced solid tumors

##### Phase 2 Dose Expansion

- Evaluate the safety and tolerability of GS-4224 in subjects with advanced solid tumors

CCI

[REDACTED]

[REDACTED]

[REDACTED]

[REDACTED]

[REDACTED]

#### 8.1.2. Primary Endpoint

The primary endpoints of this study are as follows:

##### Phase 1b Dose Escalation

- Incidence of DLT as defined in Section 3.2.

### 8.1.3. Secondary Endpoint

The secondary endpoints are as follows:

#### Phase 1b Dose Escalation

- PK parameters ( $T_{last}$ ,  $T_{max}$ ,  $C_{max}$ ,  $C_{trough}$ ,  $AUC_{last}$ ,  $AUC_{tau}$  and  $t_{1/2}$ , as applicable) for GS-4224 in subjects with advanced solid tumors

#### Phase 2 Dose Expansion

- Incidence of Grade  $\geq 3$  TEAEs in Cohort B1 subjects with advanced solid tumors
- Incidence of Grade  $\geq 3$  treatment-emergent laboratory abnormalities in Cohort B1 subjects with advanced solid tumors

CCI

[REDACTED]

[REDACTED]

CCI

[REDACTED]

[REDACTED]

[REDACTED]

[REDACTED]

[REDACTED]

[REDACTED]

## **8.2. Planned Analyses**

### **8.2.1. Interim Analysis**

#### **8.2.1.1. Analyses for Dose Escalation Decisions**

To support dose escalation decision, safety data, including DLTs and other AEs may be listed and summarized, if appropriate. Supportive data including demographic, disease history, concomitant medication, and drug administration may be listed. The analysis will occur when all subjects enrolled in a dose level have been followed for at least 21 days after the first dose of GS-4224 or two DLTs have been observed, whichever is earlier.

#### **8.2.1.2. Analyses for Dose Expansion Decisions**

To support dose expansion decision, available and relevant clinical data from all subjects treated in the escalation phase may be listed and summarized, if appropriate. The analysis will occur when all subjects enrolled in the last cohort of dose escalation phase have been followed for at least 21 days after the first dose of GS-4224 or two DLTs have been observed, whichever is earlier.

